#### **Expected outcomes**

It would be expected from this pilot study that the provision of a pictorial report of the participants oral health with tailored oral health instruction used as a "tailored" patient education tool demonstrating effective oral hygiene techniques, would improve participants' oral health. The improvement will be demonstrated with decreased plaque and MGI scores. It is also expected that the intra-oral camera will have a similar accuracy in measuring participants plaque scores compared to traditional method using dye to highlight plaque.

#### Safety measures related to Covid-19

In response to the current coronavirus pandemic, a number of measures have put in place to protect the participants and the study staff from risk of Covid-19 infection. The study will operate to current Public Health England and the Chief Dental Officer England guidelines relating to the use of PPE, social distancing and patient flow through the surgery, disinfection and Covid-19 symptom checks. Before any study activities, all study staff will be trained in the new guidelines and any subsequent updates.

For the participants, prior to their initial appointment (Visit 1, screening), they will be sent a letter from the study team by either email or post to outline the social distancing and safety measures employed at the study site. The letter will provide details as to what the participant can expect when they attend the study site and what processes they will need to follow from when they arrive to when they leave the study site. By sending the information in advance, the participants will have time to ask any questions they may have about what they will be required to do in advance of the appointment.

The study staff will also contact participants approximately 24-48 hours prior to each of their scheduled appointments (Visits 1-4 inclusive) to assess the participants current Covid status. This screening will be performed by telephone using a checklist and the responses will be charted, following the answers will be risk assessed prior to confirmation of the appointment. This is to ensure the risk of transmission of Covid-19 is minimised for both the participants and study team.

#### Reporting adverse events and serious adverse events

AEs will be reported from the time a signed and dated informed consent form is obtained until the participant completes the last study-related procedure. Those occurrences meeting the definition of SAEs will be reported using the UH Bristol Serious Adverse Event Form, including SAEs spontaneously reported to the Investigator within 30 days after the participant has completed the study (including post study follow-up). UH Bristol, on behalf of the Sponsor, will evaluate any safety information that is spontaneously reported by a Principal Investigator (PI) beyond the time frame specified in the protocol.

All AEs, regardless of seriousness, severity, or presumed relationship to study treatments, will be recorded in the source document and the CRF, together with any measures taken. The PI will record in the CRF their opinion concerning the relationship of the adverse event to study therapy. UH Bristol, on behalf of the Sponsor, assumes responsibility for appropriate reporting of adverse events to the regulatory authorities.

#### **Reporting Adverse events**

AEs will be recorded in the AE section of the CRF.

#### Reporting serious adverse events

All SAEs will be reported to the UH Bristol contact ([name]) by investigational staff within 24 hours of their knowledge of the event. All SAEs that have not resolved by the end of the study, or that have not resolved upon discontinuation of the participant's participation in the study, will be followed until any of the following occurs:

- the event resolves
- the event stabilizes
- the event returns to baseline, if a baseline value is available
- the event can be attributed to agents other than the study drug or to factors unrelated to study conduct
- when it becomes unlikely that any additional information can be obtained (participant or health care practitioner refusal to provide additional information, lost to follow-up after demonstration of due diligence with follow-up efforts)

The death of a participant is considered an SAE, as is any event requiring hospitalization (or prolongation of hospitalization) that occurs during the course of a participant's participation. Exceptions to this are hospitalizations for:

- social reasons in absence of an adverse event
- the in-clinic protocol procedures
- surgery or procedure planned before entry into the study (must be documented in the CRF)

#### Follow-up of adverse events and serious adverse events

After the initial report, the investigator will be required to proactively follow up with each participant and provide further information on the participant's condition. All AEs/SAEs will be followed until resolution, until the condition stabilizes, until the event is otherwise explained, or until the participant is lost to follow-up. The investigator may be required to obtain additional laboratory tests or investigations, and/or provide the University of Bristol with additional documentation, including autopsy reports.

#### **Ethical and Regulatory Aspects**

#### Local Regulations/Declaration of Helsinki

The Principal Investigator will ensure that this study is conducted in full conformance with the laws and regulations of the country in which the research is conducted and the Declaration of Helsinki.

#### **Informed Consent**

It is the responsibility of the investigator, or designee, to obtain written (signed and dated by the participant) informed consent from each individual in this study. Major/substantial amendments to the protocol that affect the scope of the study at the participant level will be reflected in the consent form and active participants re-consented.

#### Independent Ethics Committee

This study has been reviewed and given a favourable opinion by an independent UK NHS Research Ethics Committee. Any amendments will be reviewed by the Sponsor prior to submission for approval by the NHS Research Ethics Committee.

#### Study Data

Each participant will be assigned and identified by a unique Screening Number. Any reference made to an individual participant within the study must be done using the unique Screening Number.

All participant data recorded as part of the protocol will be recorded in participant specific case report forms (CRF). Scans recorded of the participants mouth will saved on University computers which are password protected. These scans will not be used outside of the study protocol.

For each participant who has given informed consent and has been screened, a CRF must be completed and signed by the Principal Investigator (or authorized designee) to certify that the data are complete and correct.

In order to protect the privacy of subjects, no Personally Identifiable Information (PII) (including the subject's name or initials or birth date) is to be recorded in the CRF or as part of the query text.

Adverse events and concomitant medications terms (if applicable) will be recorded in the CRF.

All data recoded will be archived securely for a period of 15 years following the end of the study.

#### Monitoring of the Study

The University of Bristol has a policy for monitoring 10% of studies. Monitoring of studies is conducted in accordance with UH Bristol monitoring policy in relation to the service level agreement with the University of Bristol.

#### Insurance

The University of Bristol has arranged Public Liability insurance to cover the legal liability of the University as Research Sponsor in the eventuality of harm to a research participant arising from management or design of the research by the University, and the policy provides policy provides an indemnity their employees for their potential liability for harm to participants during the conduct of the research.

In addition, [name] and [name] hold honorary appointments with University Hospitals Bristol NHS Foundation Trust giving them the protection of the NHS indemnity scheme.

#### Conflict of Interest and publication

The investigators have no conflict of interest with regards to this study. Data from this study will be published in a peer reviewed journal.

#### Reimbursement

As a thank you for taking part in the study, all participants will be provided with an electric toothbrush at the end of the study. No financial alternatives will be provided.

# Appendix 1: Patient Questionnaires for Visit 1 Patient Oral Health Questionnaire- Visit 1 – Part A

If you have trouble completing this questionnaire, please ask a member of staff to assist you.

1.	What is your date of birth D D M M Y Y Y Y
2.	How old are you?
3.	identify my gender as
	Man
	Woman
	Prefer not to disclose
4.	How many times per day do you regularly brush your teeth? (Please tick one box only, Less than once a day
	Once a day
	Twice a day
	More than twice a day
5.	When do you normally brush your teeth? ( Please tick all that apply )
	In the morning
	in the evening
	During the day
6.	Did you usually brush your teeth (Please tick one box only)
	Before breakfast
	Neither before or after breakfast
	After breakfast
	Both before and after breakfast

7. Which kind of toothbrush did you use the most often? (*Please tick one box only*)

8. Are you right-handed or left-handed?

(Please tick one box only)

Right-handed	
Left handed	
Both	

9. Do you currently use a toothpaste?

YES	
NO	

If yes, which toothpaste do you currently use? \_\_\_\_

10.Do your gums bleed when you brush your teeth?

YES	
NO	
11.	Do you think you have bad breath?

Occasionally

12. Do you use any of the following additional teeth cleaning aids? (*examples are shown below, please tick the box next to any you have used or if you use none of these, tick none*)

14. Are you currently concerned about your oral health?

YES	
NO	

15. If yes, what are your concerns?

Condition of teeth	
Function of teeth	
Appearance	
Breath	
Sensitivity	
Other/Not sure	
None	

16. How would you rate your current oral health?

Excellent	
Very good	
Good	
Fair	
Poor	
Not sure	

17. Are you motivated in maintaining oral health?

Very motivated	
Fairly motivated	
Neither motivated or not motivated	
Not motivated	
Not sure	

## Patient Oral Health Attitudes Questionnaire- Visit 1 – Part B

On a scale of 1 to 10, with 1 as 'Not at all' and 10 as 'extremely so' please rank the following statements accordingly:

1.	Do you	think blee	eding gur	ns and g	um disea	ase is a s	serious	health	conce	ern
	1	2	3	4	5	6	7	8	9	10
N	lot at all									Extremely so
2.	lf my ble disease	eding gui in the futi	ms are le ure is hig	ft untrea h	ted the li	kelihood	that I	will dev	velop ç	gum
	1	2	3	4	5	6	7	8	9	10
N	lot at all									Extremely so
3.	Followin mouth a	ig my Ora nd reduce	l Health p e my risk	olan over of devel	r the next oping gu	t 4 week m disea	s will ir se	nprove	the he	ealth of my
	1	2	3	4	5	6	7	8	9	10
N	lot at all									Extremely so
4.	l know l	can follow	v my Ora	l Health I	plan ove	r the nex	t 4 wee	eks		
	1	2	3	4	5	6	7	8	9	10
Ν	lot at all									Extremely so
5.	Followin	ig my Ora	l Health p	olan will	be difficu	ult to do.				
	1	2	3	4	5	6	7	8	9	10
Ν	lot at all									Extremely so
6.	6. My gum disease concerns me									
	1	2	3	4	5	6	7	8	9	10
Ν	lot at all									Extremely so

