#### Introduction

According to the General Dental Council in the UK, it is the responsibility of the dental care team to provide patients with comprehensive and accurate preventative education and instruction in a manner which encourages their self-care and motivation (General Dental Council UK, 2012). Poor oral heath in patients is commonly reflected in dental plaque induced diseases, such as periodontal (gum) disease and dental caries (tooth decay). The accumulation of dental plaque and change in the dental microflora can lead to gingival inflammation, which in turn may progress to chronic periodontal disease and the eventual loss of affected teeth (Holt et al., 2000).

Plaque removal from teeth is a skill that can be accomplished only when a patient understands the goals of plaque removal and has been appropriately educated in practicing effective dental hygiene, including correct toothbrushing and the use of interdental cleaning tools. In recent years, cognitive behavioural techniques, such as the formation of goals, actions and written coping plans have been integrated with dental hygiene intervention (Philippot et al., 2005) and were found to be more effective than verbal oral hygiene instructions (Renz et al., 2007). Kreuter (2000) concluded that patient specific tailoring of treatment related to individual goals, may be more effective in reaching the health goals than the generalised "targeting approach" and suggested defining the term tailoring as: "any combination of information or change strategies intended to reach one specific person, based on characteristics that are unique to that person, related to the outcome of interest, and have been derived from an individual assessment". Thus, patient specific oral hygiene instructions (OHI) could be more effective than generic standardised OHI, particularly in the control of periodontal disease.

Oral health educators have important and valuable role within dental practices to promote good oral health care and work with patients to prevent disease such as gingivitis (reversible gum disease) and periodontitis (irreversible gum disease). Oral hygiene instructions (OHI) given by an oral health educator make a patient more aware of periodontal disease and consequently improve gingival health.

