#### Inclusion Criteria

- Be aged 18 years and over, of either gender and in good health.
- Participants should be dentate with a minimum of 18 scorable teeth, with at least 4 teeth in the upper anterior sextant.
- Participants should be without removable dental prostheses or fixed or removable orthodontic appliances
- Be willing and competent (verbally and cognitively) to give written informed consent and complete a medical history form.
- Be willing and physically able to carry out all study procedures.
- Have an MGI score of ≥1 on at least one of the 2 identified teeth for assessment.

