#### Patient Oral Health Attitudes Questionnaire- Visit 2 – Part B

On a scale of 1 to 10, with 1 as 'Not at all' and 10 as 'extremely so' please rank the following statements accordingly:

- 7. Do you think bleeding gums and gum disease is a serious health concern 1 2 3 4 5 6 7 8 9 10 Not at all Extremely SO 8. If my bleeding gums are left untreated the likelihood that I will develop gum disease in the future is high 1 2 3 4 5 6 7 8 9 10 Not at all Extremely
- 9. Following my Oral Health plan over the last 4 weeks has improved the health of my mouth and reduce my risk of developing gum disease

1	2	3	4	5	6	7	8	9	10
Not at all									Extremely so

10. I know I can continue to follow my Oral Health plan in the future

1	2	3	4	5	6	7	8	9	10
Not at all									Extremely
									SO

11. Following my Oral Health plan will be difficult to maintain.

1	2	3	4	5	6	7	8	9	10
Not at all									Extremely so
12. My gun	n disease	concern	s me						
1	2	3	4	5	6	7	8	9	10
Not at all									Extremely so

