#### **Gingival Health**

Gingival health will be assessed using the Modified Gingival Index (Lobene, 1986) which is a non-invasive visual evaluation of gingival health. Each site (2 per tooth) will be classified as healthy or exhibiting gingivitis. If the site exhibits gingivitis the MGI index will be used to assess the degree of inflammation at 2 sites (buccal and lingual/palatal) of all scorable teeth and scored on a 5-point scale as follows:

- 0 = normal (absence of inflammation)
- 1 = mild inflammation (slight change in colour, little change in texture) of any portion of the gingival unit
- 2 = mild inflammation of the entire gingival unit
- 3 = moderate inflammation (moderate glazing, redness, oedema, and/or hypertrophy) of the gingival unit

4 = severe inflammation (marked redness and oedema/hypertrophy, spontaneous bleeding, or ulceration) of the gingival unit.

Bleeding on probing is assessed using the gingival bleeding index (BOP) as described by Ainamo & Bay (1975) and will also assess gingival health. A periodontal probe with a 0.5 mm diameter tip is inserted into the gingival crevice and swept from distal to mesial, around the tooth at an angle of approximately 60° while in contact with the sulcular epithelium. For each tooth assessed, a binary recording of either YES (bleeding observed) or NO (no bleeding observed) for bleeding will be made at 4 sites per tooth. The proportion of bleeding sites compared to all examined sites will provide the percentage of bleeding per participant.

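### Attitude item 2/8 presupposes bleeding gums that entry does not require, and a low rating on item 12 at Visit 2 cannot separate low concern from gingivitis that has cleared

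*Protocol*

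**What the plan says.** Patient attitude to oral health, measured at both visits, is a named secondary outcome (Protocol, Outcomes, Secondary Objectives). Statistical Analyses plans to analyse each secondary outcome much like the primary one, with 95% confidence intervals and p-values.

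The instrument is Part B of the questionnaires in Appendices 1 and 2. It has six items, numbered 1 to 6 at Visit 1 and 7 to 12 at Visit 2, rated "On a scale of 1 to 10, with 1 as 'Not at all' and 10 as 'extremely so". Two items take a condition as given:

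- Item 2/8: "If my bleeding gums are left untreated the likelihood that I will develop gum disease in the future is high"
- Item 6/12: "My gum disease concerns me"

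The only gingival entry criterion is "Have an MGI score of ≥1 on at least one of the 2 identified teeth for assessment" (Inclusion Criteria). Part A at Visit 1 asks "Do your gums bleed when you brush your teeth" and accepts NO. Part A at Visit 2 asks the same about the present. Of the trial's result, Expected outcomes says: "The improvement will be demonstrated with decreased plaque and MGI scores".

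**The concern.** An attitude item is usable if a given rating means the same thing for everyone who gives it. Item 2/8 asks about the consequence of a condition that some participants may truthfully have denied in Part A of the same questionnaire. Such a participant can answer hypothetically, answer 1 because the statement does not fit, or leave it blank, and the form does not show which.

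Item 12 has a different problem. Its premise can stop being true between the two visits, and the trial hopes that gingival health will improve over that interval. A fall from item 6 to item 12 may then be good news (the disease has gone) or bad news (the participant has lost interest). Randomisation does not remove this, because clinical response comes after randomisation and is what the intervention is meant to change. If one arm responds better, its rated concern may fall further with no difference in attitude.

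**Working it through.** The protocol states no figure on this point, so there is none to reproduce. The check sets the passages side by side.

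**Item 2/8, both visits**

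1. Inclusion Criteria contains no bleeding criterion.
2. Part A (question 10 at Visit 1, question 4 at Visit 2) lets participants answer NO on bleeding. The clinical assessments likewise allow a NO for bleeding on probing at each of 4 sites per tooth.
3. Part B has only the ten-point scale. Several Part A questions offer a not-sure or none option, and Appendix 3 offers a do-not-know option.
4. A participant can therefore deny bleeding in Part A and still have to rate a statement about their own bleeding gums in Part B. For that person the premise is false.

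**Item 6, Visit 1**

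1. Appendix 4 grades 0 as normal and defines the next grade as "1 = mild inflammation (slight change in colour, little change in texture) of any portion of the gingival unit".
2. A site is classed as healthy or as showing gingivitis, and the Introduction's gloss is "gingivitis (reversible gum disease".
3. Entry needs MGI of at least 1 on one of the two teeth, so every eligible participant has gum disease on the protocol's own terms. The premise holds for all.

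**Item 12, Visit 2**

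1. The protocol calls gingivitis reversible and expects MGI to fall, so some participants may be at grade 0 by week 4.
2. For them a rating of 1 is compatible with no disease and with no interest in it.

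**Illustration only; the rates and ratings are assumptions**

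*Non-bleeders.* If a proportion p of eligible participants do not bleed, the expected number among 20 is 20p, and the chance of at least one is 1 − (1 − p)^20.

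| p | Expected number | Chance of at least one |
|---|---|---|
| 5% | 1 | 64% |
| 10% | 2 | 88% |
| 20% | 4 | 99% |
| 30% | 6 | over 99% |

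*Item 12.* Suppose participants whose gingivitis clears answer 1, everyone else keeps their Visit 1 rating b, and the proportions clearing are r_T (test) and r_C (control). The between-arm difference in change is −(r_T − r_C)(b − 1).

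| b | r_C 10%, r_T 30% | r_C 20%, r_T 50% or r_C 30%, r_T 60% |
|---|---|---|
| 4 | −0.2 × 3 = −0.6 | −0.3 × 3 = −0.9 |
| 6 | −0.2 × 5 = −1.0 | −0.3 × 5 = −1.5 |
| 8 | −0.2 × 7 = −1.4 | −0.3 × 7 = −2.1 |

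The tables show direction and mechanism. They do not estimate what this trial would see. If the arms respond equally and b is the same in both, the between-arm artefact is zero, although change within each arm is still hard to interpret.

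**The case against.** The strongest reply is that the items can be answered and that the trial already collects what is needed to read them. Item 2/8 is a conditional and can be taken hypothetically. A rating of 1 on item 12 is a usable answer for someone without disease. Self-reported bleeding, concern about oral health and self-rated oral health are asked at both visits, alongside clinical MGI and bleeding. The Visit 2 list also puts the questionnaire before the final scan and gingival assessment. In that order item 12 reflects what participants notice themselves, and those who have healed unawares will not change their rating for that reason.

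Much of this stands. The fault is ambiguity, not the absence of any possible answer, and the Part A data help with item 8. They help less with item 12, because Part A does not ask whether the participant believes that they have gum disease, and MGI covers only two upper front teeth. The visit order weakens the mechanism but does not remove it, since participants can notice that bleeding or redness has gone.

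Several stronger readings are tempting but not supported:

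- *Item 6 is invalid at Visit 1.* It is not, for the reason shown above.
- *MGI grade 1 means no bleeding.* The MGI is a visual index, with bleeding recorded separately. That spontaneous bleeding is named only at grade 4 says nothing about bleeding on brushing or probing at lower grades. The point rests on the absence of a bleeding criterion and on Part A.
- *The intervention is meant to cure.* The protocol speaks of improvement and lower scores.
- *Items 2/8 and 6/12 contradict each other.* The Introduction describes gingival inflammation progressing to chronic periodontal disease, so present gingivitis and a future risk of worse disease can coexist.

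**Conclusion.** The point holds in a limited form. Item 2/8 has a false premise at either visit for any participant whose gums do not bleed. Item 12 is ambiguous for any participant whose gingivitis has cleared, so its change from Visit 1 mixes attitude with clinical response and could differ by arm if response differs. Item 6 at Visit 1 is valid.

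Two of the six Part B items are affected, within one secondary outcome of a 20-person pilot sized for estimation. The plaque and gingival outcomes are untouched. A reader might infer that a Part B attitude score is biased by a known amount. The documents do not support that: the protocol defines no Part B total, so only item ratings are at stake, and it gives no rate of bleeding, of clearance or of baseline concern, so the size is unknown. This is a cheap improvement to the instrument, not a threat to the trial.

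**What to change.** Either of two changes would do, applied identically at both visits.

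1. Reword both items so that they keep the personal reference without assuming a present condition. For item 2/8, for example: *If my gums bled and were left untreated, the likelihood that I would develop gum disease is high.* For item 6/12: *I am concerned about having or developing gum disease.* Wholly general statements would be a poorer choice, because they lose perceived personal risk and come close to repeating item 1/7.
2. Keep the current wording and add a box to both items reading *I do not have this*. Those who tick it at Visit 2 are then a group partly formed by clinical response, so the number ticking should be reported by arm beside the ratings.

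In either case, report the items separately and read them alongside self-reported bleeding from Part A. If the forms are already in use, this separate reporting can still be done, with the ambiguity of item 12 stated.

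The cost is a minor amendment to two questionnaire pages. Rewording also slightly changes what the two items measure.
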